5.1.4.2.4 Management of Hy's Law Cases

In the event a patient develops concurrent increase in AST and/or ALT \geq 3 × ULN, bilirubin \geq 2 × ULN but without concurrent increases in alkaline phosphatase (i.e., alkaline phosphatase < 2 × ULN), that is not attributable to liver metastases or biliary obstruction, investigational study treatment should be permanently discontinued.

5.1.4.2.5 Management of Investigational Study Treatment in Event of Non-Hematological Toxicities

Per protocol, a complete review of adverse events should be conducted at each clinic visit. Symptomatic Grade 2 sitravatinib-related non-hematological adverse events occurring any time on study, particularly early in treatment (e.g., Cycle 1 Day 15 or Cycle 2 Day 1), are recommended to be managed using dose reduction to the next lower dose level, per the reduction schedule outlined in Table 9, rather than continued dosing until interruption becomes necessary.

Non-hematological toxicities \geq Grade 3 and considered to be treatment-related should be managed with investigational study treatment interruption until resolution of toxicity to \leq Grade 1 or to baseline value. If the toxicity is adequately managed by routine supportive care (such as electrolyte supplementation), treatment may be resumed at the same dose; if not, treatment may be resumed at a reduced dose (Table 15). Treatment with sitravatinib may continue without dose modification (e.g., interruption or reduction) in cases of asymptomatic amylase and/or lipase increases in the absence of other clinical evidence of pancreatitis (e.g., symptoms, electrolyte abnormalities, radiographic changes) at the investigator's discretion. Recurrence of the toxicity may be managed similarly. If treatment is interrupted for \geq 28 days, permanent discontinuation from sitravatinib should be considered.

Table 15: Investigational Study Treatment Dose Modifications – Non-Hematological Drug-Related Toxicities^{1, 2}

Toxicity	Treatment Delay	Dose Modification
Grade 1	Continue treatment unchanged	
Grade 2 Asymptomatic	May be implemented based on Investigator or patient discretion ²	
Grade 2 Symptomatic	May be implemented based on Investigator or patient discretion ² Early dose reduction to the next lower dose level is recommended over treatment interruption	
Grade 3 or 4	Hold until ≤ Grade 1 or return to baseline ²	Resume at dose one or more levels below that inducing the toxicity. Exceptions presented in footnote. ^{2,3}

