Management of selected adverse events for each investigational study treatment are presented in Sections 5.1.1.4, 5.1.2.4 and 5.1.3.4.

The current OPDIVO® US Prescribing Information (USPI OPDIVO [nivolumab]) must be consulted to determine appropriate dose modifications for nivolumab.

Patients may resume at the same dose in the following cases:

- a. Grade 3 or 4 electrolyte abnormality that is not clinically complicated and resolves spontaneously or with conventional medical treatment within 72 hours;
- b. Grade 3 amylase or lipase elevation that is not associated with symptoms or other clinical manifestations (e.g., electrolyte abnormalities, radiographic changes) of pancreatitis.

5.1.4.2.6 Management of Investigational Study Treatment in Event of Hematological Toxicities

Hematological toxicities are not a frequent cause of treatment interruption or discontinuation with any of the three investigational study treatments. Observed \geq Grade 3 hematological events that are considered to be causally related to the administered investigational study treatment should be managed using treatment interruption or dose reduction at the discretion of the Investigator. If treatment is interrupted for \geq 28 days, permanent discontinuation from study treatment should be considered.

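### For asymptomatic amylase/lipase rises on sitravatinib, Section 5.1.4.2.5 and Table 15 conflict at Grade 4, and Table 15 omits at Grade 3 the text's permission to continue dosing

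*Protocol*

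**What the plan says.** Protocol Section 5.1.4.2.5 sets a general rule and then a narrower permission in the same paragraph. Under the general rule, non-hematological toxicities of Grade 3 or higher "considered to be treatment-related should be managed with investigational study treatment interruption until resolution of toxicity to" Grade 1 or baseline. Dosing may then restart at the same dose if routine supportive care controls the toxicity, and otherwise at a reduced dose under Table 15.

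The permission reads: "Treatment with sitravatinib may continue without dose modification (e.g., interruption or reduction) in cases of asymptomatic amylase and/or lipase increases". It applies "in the absence of other clinical evidence of pancreatitis (e.g., symptoms, electrolyte abnormalities, radiographic changes) at the investigator's discretion". It names sitravatinib only and no CTCAE grade.

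Table 15 covers all the investigational agents. For Grade 3 or 4 its delay column says "Hold until ≤ Grade 1 or return to baseline" and its dose column says "Resume at dose one or more levels below that inducing the toxicity. Exceptions presented in footnote". The footnote lists the cases in which patients may restart at the same dose. Item a, on uncomplicated electrolyte abnormalities, names Grades 3 and 4. Item b reads "Grade 3 amylase or lipase elevation that is not associated with symptoms or other clinical manifestations" of pancreatitis, and so names Grade 3 only.

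**The concern.** A site facing an asymptomatic, treatment-related Grade 4 lipase rise can find two answers. The text lets the investigator continue at the current dose. The table tells the investigator to hold and then return at a lower dose, and none of its listed exceptions applies. At Grade 3 the table also holds, and the footnote deals only with the dose at restart.

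The main stake is consistent handling of a possible pancreatic toxicity. The secondary stake is descriptive safety output:

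- SAP Section 11.1.7.2 tabulates TEAEs leading to dose reduction or interruption.
- SAP Section 8.3.4 sets relative dose intensity as dose received over starting daily dose times duration, so it falls with each hold or reduction.
- SAP Section 8.3.5 adjusts compliance for AE-related interruptions and reductions.
- Protocol Section 8.2.1 makes a change in study dosing one of the criteria for recording an abnormal laboratory value as an AE. If no other criterion is met, the passage a site follows can decide whether an asymptomatic rise is recorded as an AE at all.

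**Working it through.** The plan states no figure to reproduce on this point. The check sets the passages side by side for one case: a treatment-related, asymptomatic amylase or lipase rise on sitravatinib with no other evidence of pancreatitis.

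| Grade | Section 5.1.4.2.5 permission | Table 15 and footnote | Result |
|---|---|---|---|
| 1 | May continue unchanged | Continue unchanged | No conflict |
| 2 | May continue unchanged | Delay or change is discretionary | No conflict |
| 3 | May continue with no hold and no reduction | Hold; footnote b then allows the same dose | Differ on the hold; dose agrees |
| 4 | May continue with no hold and no reduction | Hold; restart at least one level lower; no exception listed | Differ on the hold and on the dose |

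Four steps support the two lower rows.

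1. Footnote b is about restarting, which presupposes that dosing stopped. It waives the reduction, not the hold.
2. Item a names Grades 3 and 4 while item b names only Grade 3. On its face, then, the table leaves Grade 4 enzyme rises under the default.
3. Combining the passages at Grade 4 gives an odd outcome: an investigator who does not interrupt may stay at full dose, while one who holds must come back lower.
4. No other passage settles it. The general rule's same-dose route depends on control by supportive care and does not mention these enzymes. Section 5.1.2.4, on sitravatinib-specific events, has no amylase or lipase entry.

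**Frequency.** The inputs are Protocol Table 5 and the accompanying text in Section 1.5.3.2.1 (Study 516-001, sitravatinib alone, N = 153):

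- Grade 3 or higher lipase increase: 6/153 = 3.9% (shown as 4%).
- Grade 3 or higher amylase increase: 2/153 = 1.3% (shown as 1%).
- Related Grade 4 lipase increase: 1/153 = 0.65% (shown as 0.7%).

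If no patient had both enzymes raised, the first two together give at most (6 + 2)/153 = 5.2%. These counts are not restricted to asymptomatic cases.

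**The case against.** The strongest defence is that this is a default with a specific exception. The permission follows closely on the general rule in the same paragraph. It is narrower in drug, event and condition, and it permits rather than commands. At Grade 3 this largely works: an investigator who uses the discretion continues, one who holds applies footnote b, and both keep the same dose. What remains at Grade 3 is that Table 15 says where its exceptions are and does not list this one. At Grade 4 the defence fails, because the table requires a lower dose at restart and the text requires neither a hold nor a reduction.

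A reader might infer more than the documents support, in three ways.

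- *That the protocol expressly allows dosing through an enzyme rise of any grade.* It does not say so. The absence of a grade limit is silence, and the permission carries two conditions and names one drug.
- *That about 5 to 7 patients in the expanded cohort would meet conflicting instructions*, from 125 × 6/153 = 4.9 and 125 × 8/153 = 6.5. The counts include symptomatic cases, and Table 5 also lists pancreatitis in 3 patients. They come from monotherapy, with dose escalation spanning 10 to 200 mg daily. Section 1.5.3.2.2 also shows 70 sitravatinib patients (CIT-experienced and CIT-naïve) treated by 26 June 2018, before the 16 May 2019 letter changed this section and before Amendment 5 updated Table 15. The documents do not show that all 125 were treated under the current wording. The figure is at most an illustrative upper value. The Grade 4 case alone gives 125 × 1/153 = 0.8.
- *That efficacy is affected.* Nothing here enters the ORR definition or its test.

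It is also fair to say that dose handling is already discretionary in places, such as Grade 2 delays in Table 15 and re-challenge in Section 5.1.2.3. A few discordant cases would therefore change the exposure tables little.

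**Conclusion.** The point holds as a minor internal inconsistency. At Grade 4 the text and Table 15 cannot both be followed as written whenever the investigator uses the permission: they differ on the hold and on the dose afterwards. At Grade 3 the passages can be read together, but Table 15 does not show the permission on which that reading depends.

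The relevant events are uncommon, and the Grade 4 evidence is a single related lipase event in 153 monotherapy patients, whose symptoms are not described. The effect on dose intensity cannot be quantified from the documents.

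Two assumptions matter. The missing grade limit in the text is taken to leave Grades 3 and 4 within the permission. The footnote numbers are not legible beside the notes, so the same-dose note is matched to the dose column by its order; that the hold carries no enzyme exception is likely on that basis, but not certain.

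**What to change.** The sponsor should reconcile the Section 5.1.4.2.5 text, the Grade 3 or 4 row of Table 15 and footnote b, so that each grade of asymptomatic amylase/lipase rise has one consistent instruction on holding and on the dose at resumption. If the text is meant as an exception to the table, the table should point to it and the grades covered should be stated. Which rule applies is for the sponsor to decide.

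The cost is clarification wording, issued as an administrative letter or amendment under Section 13.1. This point requires no change to the sample size, the ORR analysis or data collection.

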5.2 Nivolumab Study Drug

Nivolumab will be obtained from commercial sources and managed in accordance with the OPDIVO US Prescribing Information. The following sections provide reprints of information and guidance included in the OPDIVO US Prescribing Information dated April 2018. Refer to the current OPDIVO US Prescribing Information provided by the manufacturer for updates during the conduct of this clinical trial (https://packageinserts.bms.com/pi/pi_opdivo.pdf).

5.2.1 Formulation and Packaging

OPDIVO is a sterile, preservative-free, non-pyrogenic, clear to opalescent, colorless to pale-yellow liquid that may contain light (few) particles. OPDIVO injection for intravenous infusion is supplied in single-dose vials. Each mL of OPDIVO solution contains nivolumab 10 mg, mannitol (30 mg), pentetic acid (0.008 mg), polysorbate 80 (0.2 mg), sodium chloride (2.92 mg), sodium citrate dihydrate (5.88 mg), and Water for Injection, USP. The formulation may contain hydrochloric acid and/or sodium hydroxide to adjust pH to 6.

5.2.2 Preparation and Dispensing

Visually inspect drug product solution for particulate matter and discoloration prior to administration. OPDIVO is a clear to opalescent, colorless to pale-yellow solution. Discard the vial if the solution is cloudy, discolored, or contains extraneous particulate matter other than a few translucent-to-white, proteinaceous particles. Do not shake the vial.

- Withdraw the required volume of OPDIVO and transfer into an intravenous container.
- Dilute OPDIVO with either 0.9% Sodium Chloride Injection, USP or 5% Dextrose Injection, USP to prepare an infusion with a final concentration ranging from

1 mg/mL to 10 mg/mL. For patients with weight less than 40 kg, the total volume of infusion must not exceed 4 mL/kg.

- Mix diluted solution by gentle inversion. Do not shake.
- Discard partially used vials or empty vials of OPDIVO.

The product does not contain a preservative. After preparation, store the OPDIVO infusion either:

- at room temperature for no more than 4 hours from the time of preparation. This includes room temperature storage of the infusion in the IV container and time for administration of the infusion or
- under refrigeration at 2°C to 8°C (36°F to 46°F) for no more than 24 hours from the time of infusion preparation.

Do not freeze.

5.2.3 Administration

The recommended dose of OPDIVO is 240 mg every 2 weeks (Q2W) or 480 mg every 4 weeks (Q4W) administered as an intravenous infusion over approximately 30 minutes, until disease progression or unacceptable toxicity. Administer the OPDIVO infusion through an intravenous line containing a sterile, non-pyrogenic, low protein binding inline filter (pore size of 0.2 micrometer to 1.2 micrometer). Flush the intravenous line at end of infusion.

5.2.4 Infusion Modification and Discontinuation

There are no recommended dose modifications for hypothyroidism or hyperthyroidism.

Interrupt or slow the rate of infusion in patients with mild or moderate infusion reactions. Discontinue OPDIVO in patients with severe or life-threatening infusion reactions.

Dose modifications recommended in OPDIVO US Prescribing Information dated April 2018 are reprinted in Table 16. Required dose modifications (i.e., interruption or discontinuation) for nivolumab should be performed per the current OPDIVO US Prescribing Information (USPI OPDIVO [nivolumab]) Section 2.10 and Section 5, in addition to potential dose modifications for sitravatinib in accordance to Section 5.1.2.3.

Table 16: Recommended Dose Modifications for OPDIVO – Reprinted from OPDIVO US Prescribing Information

Adverse Reaction	Severity *	Dose Modification	
Colitis	Grade 2 diarrhea or colitis	Withhold dose ^a	
	Grade 3 diarrhea or colitis		
	Grade 4 diarrhea or colitis	Permanently discontinue	
Durannanitia	Grade 2 pneumonitis	Withhold dose a	
Pneumonitis	Grade 3 or 4 pneumonitis	Permanently discontinue	
Hepatitis	Aspartate aminotransferase (AST)/or alanine aminotransferase (ALT) more than 3 and up to 5 times the upper limit of normal or total bilirubin more than 1.5 and up to 3 times the upper limit of normal	Withhold dose b	
	AST or ALT more than 5 times the upper limit of normal or total bilirubin more than 3 times the upper limit of normal	Permanently discontinue	
Uymanhygitig	Grade 2 or 3 hypophysitis	Withhold dose ^a	
Hypophysitis	Grade 4 hypophysitis	Permanently discontinue	
Adrenal	Grade 2 adrenal insufficiency	Withhold dose a	
Insufficiency	Grade 3 or 4 adrenal insufficiency	Permanently discontinue	
Type 1 Diabetes	Grade 3 hyperglycemia	Withhold dose a	
Mellitus	Grade 4 hyperglycemia	Permanently discontinue	
Nephritis and Renal	Serum creatinine more than 1.5 and up to 6 times the upper limit of normal	Withhold dose ^a	
Dysfunction	Serum creatinine more than 6 times the upper limit of normal	Permanently discontinue	
Skin	Grade 3 rash or suspected Stevens-Johnson syndrome (SJS) or toxic epidermal necrolysis (TEN)	Withhold dose ^a	
	Grade 4 rash or confirmed SJS or TEN	Permanently discontinue	
Encephalitis	New-onset moderate or severe neurologic signs or symptoms	Withhold dose ^a	
•	Immune-mediated encephalitis	Permanently discontinue	
Other	Other Grade 3 adverse reaction		
	First occurrence	Withhold dose ^a	
	Recurrence of same Grade 3 adverse reactions	Permanently discontinue	
	Life-threatening or Grade 4 adverse reaction	Permanently discontinue	
	Grade 3 myocarditis	Permanently discontinue	
	Requirement for 10 mg per day or greater prednisone or equivalent for more than 12 weeks	Permanently discontinue	
	Persistent Grade 2 or 3 adverse reactions lasting 12 weeks or longer	Permanently discontinue	

- * Toxicity was graded per National Cancer Institute Common Terminology Criteria for Adverse Events. Version 4.0 (NCI CTCAE v4).
- a Resume treatment when adverse reaction returns to Grade 0 or 1.
- b Resume treatment when AST/ALT returns to baseline.

5.2.5 Nivolumab Adverse Event Management Guidelines

Table 17 reproduces AE management guidelines provided in OPDIVO US Prescribing Information, Section 5.

Table 17: Management of Nivolumab Immune-Related Adverse Events – Reprinted from OPDIVO US Prescribing Information

Immune-mediated AE Defined as Requiring Use of Corticosteroids and no Clear Alternate Etiology		
Immune-mediated pneumonitis	Monitor patients for signs with radiographic imaging and symptoms of pneumonitis. Administer corticosteroids at a dose of 1 to 2 mg/kg/day prednisone equivalents for moderate (Grade 2) or more severe pneumonitis, followed by corticosteroid taper. Permanently discontinue nivolumab for severe (Grade 3) or life-threatening (Grade 4) pneumonitis and withhold nivolumab until resolution for moderate (Grade 2) pneumonitis.	
Immune-mediated colitis	Administer corticosteroids at a dose of 1 to 2 mg/kg/day prednisone equivalents followed by corticosteroid taper for severe (Grade 3) or life-threatening (Grade 4) colitis. Administer corticosteroids at a dose of 0.5 to 1 mg/kg/day prednisone equivalents followed by corticosteroid taper for moderate (Grade 2) colitis of more than 5 days duration; if worsening or no improvement occurs despite initiation of corticosteroids, increase dose to 1 to 2 mg/kg/day prednisone equivalents. Withhold OPDIVO for moderate or severe (Grade 2 or 3) colitis. Permanently discontinue OPDIVO for life-threatening (Grade 4) or for recurrent colitis upon restarting OPDIVO.	
Immune-mediated hepatitis	Administer corticosteroids at a dose of 1 to 2 mg/kg/day prednisone equivalents for severe (Grade 3) or life-threatening (Grade 4) transaminase elevations, with or without concomitant elevation in total bilirubin. Administer corticosteroids at a dose of 0.5 to 1 mg/kg/day prednisone equivalents for moderate (Grade 2) transaminase elevations. Withhold OPDIVO for moderate (Grade 2) and permanently discontinue OPDIVO for severe (Grade 3) or life-threatening (Grade 4) immune-mediated hepatitis.	
Immune-mediated endocrinopathies		
Hypophysitis	Administer hormone replacement as clinically indicated and corticosteroids at a dose of 1 mg/kg/day prednisone equivalents followed by corticosteroid taper for moderate (Grade 2) or greater hypophysitis. Withhold OPDIVO for moderate (Grade 2) or severe (Grade 3). Permanently discontinue OPDIVO for lifethreatening (Grade 4) hypophysitis.	

Table 17: Management of Nivolumab Immune-Related Adverse Events – Reprinted from OPDIVO US Prescribing Information (Continued)

Immune-mediated endocrinopathies (continued)		
Adrenal Insufficiency	Administer corticosteroids at a dose of 1 to 2 mg/kg/day prednisone equivalents followed by a corticosteroid taper for severe (Grade 3) or life-threatening (Grade 4) adrenal insufficiency. Withhold OPDIVO for moderate (Grade 2) and permanently discontinue OPDIVO for severe (Grade 3) or life-threatening (Grade 4) adrenal insufficiency.	
Hypothyroidism and Hyperthyroidism	Administer hormone-replacement therapy for hypothyroidism. Initiate medical management for control of hyperthyroidism. There are no recommended dose adjustments of OPDIVO for hypothyroidism or hyperthyroidism.	
Type 1 Diabetes Mellitus	Withhold OPDIVO in cases of severe (Grade 3) hyperglycemia until metabolic control is achieved. Permanently discontinue OPDIVO for life-threatening (Grade 4) hyperglycemia.	
Other Immune-med	liated AEs	
Immune-Mediated Nephritis and Renal Dysfunction	Administer corticosteroids at a dose of 1 to 2 mg/kg/day prednisone equivalents followed by corticosteroid taper for life-threatening (Grade 4) increased serum creatinine. Administer corticosteroids at a dose of 0.5 to 1 mg/lg/day prednisone equivalents for moderate (Grade 2) or severe (Grade 3) increased serum creatinine, if worsening or no improvement occurs, increase dose of corticosteroids to 1 to 2 mg/kg/day prednisone equivalents.	
Immune-Mediated Skin Adverse Reactions	For symptoms or signs of SJS or TEN, withhold OPDIVO and refer the patient for specialized care for assessment and treatment. If SJS or TEN is confirmed, permanently discontinue OPDIVO. For immune-mediated rash, administer corticosteroids at a dose of 1 to 2 mg/kg/day prednisone equivalents followed by a corticosteroid taper for severe (Grade 3) or life-threatening (Grade 4) rash. Withhold OPDIVO for severe	
	(Grade 3) rash and permanently discontinue OPDIVO for life-threatening (Grade 4) rash.	
Immune-Mediated Encephalitis	Withhold OPDIVO in patients with new-onset moderate to severe neurologic signs or symptoms and evaluate to rule out infectious or other causes of moderate to severe neurologic deterioration. If other etiologies are ruled out, administer corticosteroids at a dose of 1 to 2 mg/kg/day prednisone equivalents for patients with immune-mediated encephalitis, followed by corticosteroid taper. Permanently discontinue OPDIVO for immune-mediated encephalitis.	
Other Immune Mediated Adverse Reactions	For any suspected immune-mediated adverse reactions, exclude other causes. Based on the severity of the adverse reaction, permanently discontinue or withhold OPDIVO, administer high-dose corticosteroids, and if appropriate, initiate hormone-replacement therapy. Upon improvement to Grade 1 or less, initiate corticosteroid taper and continue to taper over at least 1 month. Consider restarting OPDIVO after completion of corticosteroid taper based on the severity of the event.	
Infusion Reactions	Discontinue OPDIVO in patients with severe or life-threatening infusion reactions. Interrupt or slow the rate of infusion in patients with mild or moderate infusion reactions.	

5.3 Medication Error

Medication errors may involve patient exposure to a wrong study drug, at a wrong dosing frequency, or at a wrong dose level (e.g., a dose that is not planned in the study). Medication errors occurring during the conduct of this study will be documented as AEs (regardless of whether clinical signs or symptoms are observed) and if serious consequences are observed, will be reported on Serious Adverse Event (SAE) forms. In all cases of medication error, the sponsor should be notified immediately.

There is currently no specific treatment in the event of an overdose of glesatinib, sitravatinib, mocetinostat or nivolumab. The Investigator will use clinical judgment to treat any overdose.

